2.2.2 Secondary Objectives

The secondary objective of this study is to evaluate reduction of IOP, as a PD biomarker, following different SHP639 dosing regimens.

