4.1 Inclusion Criteria

The subject will not be considered eligible for the study without meeting all of the criteria below.

Subjects cannot be enrolled or randomized before all inclusion criteria (including test results) are confirmed.

1. Subjects must provide written, signed and dated informed consent to participate in the study in accordance with the International Council for Harmonisation (ICH) Good Clinical Practice (GCP) Guideline E6 and applicable regulations, before completing any study-related procedures.
2. Subjects must be aged from 18 through 90 at the time of consent. This inclusion criterion will only be assessed at the screening visit.
3. Subjects must have OHT or stable early POAG in both eyes with acceptable Humphrey visual fields (HVF). Early POAG for this protocol is defined as healthy appearing anterior chamber angles (Shaffer classification system grade 3 or 4) and focal and/or generalized thinning of the optic disc rim characteristic of glaucomatous disease. An acceptable HVF must have been performed within approximately one year of screening, have a false-positive rate of 25% maximum, false-negative rate of 25% maximum, and fixation loss rate of 33% maximum, and mean deviation of no worse than -6.00 dB.
4. On Day -1, subjects must have a mean IOP of ≥ 24 mmHg at 8:00 AM and a mean IOP of ≥ 22 mmHg at 10:00 AM in at least 1 eye, with an IOP difference of < 4 mmHg between eyes at both of these time points. If only 1 eye meets this criterion, then it will be the designated study eye for pharmacodynamic analysis; this eye will also be used for dosing in Cohort A SDTP (designated study eye criteria are detailed in Section 3.1.1).
5. Subjects must have a best-corrected visual acuity (BCVA) in both eyes of 65 letters on the Early Treatment Diabetic Retinopathy Study chart (Snellen equivalent $\sim 20/60$) or better at the screening and baseline assessments.
6. Subjects must be males or females who are nonpregnant and nonlactating at screening (negative serum beta-human chorionic gonadotropin [β -hCG]); if sexually active during the study, they must agree to comply with the applicable contraceptive requirements (refer to Section 4.4) throughout the study period and for 60 days following the last dose of investigational product.

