4.2 Exclusion Criteria

The subject will be excluded from the study if any of the following exclusion criteria are met:

1. Subject has an anatomically narrow angle, synechiae or evidence of prior inflammation, angle closure glaucoma, normal tension glaucoma, pseudoexfoliation syndrome or pigmentary dispersion syndrome with or without glaucoma, or secondary glaucoma.
2. Subject has corneal endothelial cell counts of less than 2000 cells/mm² (measured by noncontact specular microscopy) at the screening or baseline assessments.
3. Subject has central corneal thickness less than 500 µm or greater than 620 µm at the screening or baseline assessments.
4. Subject has IOP greater than 32 mmHg in either eye before randomization.
5. Subject has used topical ocular hypotensive medications as follows: prostaglandin analogs, β-adrenoceptor antagonists, α-adrenergic agonists, or epinephrine-related medications within 4 weeks before the first dose of investigational product; or pilocarpine or carbonic anhydrase inhibitors within 7 days before the first dose of investigational product.
6. Subject has a history of angle closure, ocular surgery, microinvasive glaucoma surgery device insertion, or laser surgery, except for the following procedures, which are allowed: uncomplicated cataract surgery, laser peripheral iridotomy with resultant angle of Shaffer grade 3 or 4, and postcataract neodymium-doped yttrium-aluminum-garnet (Nd:YAG) laser posterior capsulotomy. Cataract surgery and other procedures must have occurred a minimum of 3 months before randomization.
7. Subject has a history of significant ocular trauma or ocular disease including but not limited to moderate to severe dry eye disease that requires chronic treatment or punctal plugs.
8. Subject has evidence of ocular infection, inflammation, degeneration, or dystrophy at the screening or baseline assessments, including but not limited to moderate to severe blepharitis (mild blepharitis is allowed), conjunctivitis (allergic or infectious), corneal dystrophy (epithelial, stromal, or endothelial), corneal haze of grade 1 or greater based on the Hwang Grading Scale of Corneal Haze, corneal opacities, keratitis, uveitis, or vitritis.

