2.4 Identification of Study Eye

For the purpose of overall analysis, 1 eye will be designated as the primary eye for the duration of the subject's participation in the study. In Cohort A single-dose treatment period (SDTP), the investigational product will be dosed in the designated study eye only. For all subjects participating in the multiple-dose treatment period (MDTP), a designated study eye will be also identified and the investigational product will be dosed in both eyes. For Cohort A, the study eye for MDTP will be the same as the study eye in SDTP. For SDTP Cohort A and MDTP Cohorts B, C and D, the following procedure will be used to determine the designated study eye:

- For each subject, the mean baseline IOP at a time point will be the mean of the IOPs on days -2 and -1 at that time point.
- The designated study eye will be the eye with the highest mean baseline IOP at the predose time point.
- If both eyes have equal mean baseline IOPs, the eye with the highest mean IOP at the +2-hour time point will be the designated study eye.
- If both eyes have equal mean IOPs at the +2-hour time point, the eye with the highest mean IOP at the +4-hour time point will be the designated study eye.
- If both eyes have equal mean IOPs at the +4-hour time point, the eye with the highest mean IOP at the +8-hour time point will be the designated study eye.
- If both eyes have equal mean IOPs at the +8-hour time point, the right eye will be the designated study eye.

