12.4 Pharmacodynamic Methods

All the PD analyses will be performed using the Pharmacodynamic set. Intraocular pressure (IOP; mmHg), a PD biomarker, will be measured using Goldmann applanation tonometry.

Intraocular pressure will be measured according to the following schedule:

SDTP (Cohort A only): baseline (Days -2 and -1), Days 1 and 2, at Predose, 0.5, 1, 2, 3, 4, 6, 8, and 12 h

MDTP (Cohort A only): (all cohorts): baseline (Days -2 and -1), Days 1, 2, 27, and 28, at Predose, 0.5, 1, 2, 3, 4, 6, 8, and 12 h

MDTP (all cohorts): Days 7, 14, and 21 at Predose, 2, 4, 8, and 12 h

The individual and mean absolute IOP, IOP reduction from baseline and percentage of IOP reduction from baseline versus time profiles will be presented in figures. Mean plots will be presented using nominal time and individual plots will be presented using actual time.

In addition, the relationship of percentage of IOP reduction from baseline and dose of SHP639 will be presented in a Box-and-Whiskers plot.

Percentage of IOP reduction from baseline measurements data versus time will be used to estimate the PD parameters using Phoenix® WinNonlin® version 6.4 (Certara USA, Inc., Princeton, NJ) for each individual in each treatment by eye (study eye and non-study eye). Baseline is defined as the arithmetic mean of the time-matched IOP measurements on Days -2

and -1 for that particular subject. Potential effect of diurnal change on variation in IOP is accounted for by factoring time-matched baseline in the calculations of percent of IOP reduction from baseline measurements.

Parameter	Definition
IOP reduction from baseline	IOP reduction from baseline is calculated as follows: $\frac{\text{Baseline IOP} - \text{IOP after treatment}}{\text{Baseline IOP}}$
% of IOP reduction from Baseline	Percentage of IOP reduction from baseline is calculated as follows: $\frac{(\text{Baseline IOP} - \text{IOP after treatment})}{\text{Baseline IOP}} \times 100$
E _{max}	Maximum percent IOP reduction from baseline
TE _{max}	Time of E _{max}
AUEC _{0-t}	Area under the effect curve for the percentage of IOP reduction from baseline versus time profile from time zero (predose) to the time of the last measurable percentage of IOP reduction from baseline, calculated using the linear up/log down interpolation rule.
AUEC _{0-τ}	Area under the effect curve for the percentage of IOP reduction from baseline versus time profile over a dosing interval, calculated using the linear up/log down interpolation rule.

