12.5 Statistical Analysis of Pharmacodynamic Data

Absolute IOP, IOP reduction from baseline, and percentage of IOP reduction from baseline will be listed by dose, cohort, subject, treatment period (single dose or multiple dose; Cohort A only), eye (study eye and non-study eye), study day and sample nominal time point. Descriptive summary statistics for absolute IOP, IOP reduction from baseline, percentage of IOP reduction from baseline, E_{max}, TE_{max}, AUEC_{0-t}, AUEC_{0-τ}, and AUEC_{0-∞} (n, arithmetic mean, SD, 95% CI, median, maximum, minimum, geometric mean and geometric CV%) will be calculated by dose, cohort, treatment period, eye (study eye and non-study eye), study day, and sample nominal time point (for days with multiple assessments per day).

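### In Cohorts B-D the IOP readings that select the subject and the study eye also form the multiple-dose baseline; in Cohort A they do not. Raw IOP change is therefore tilted slightly against QD, and SAP 12.5 plans no placebo-adjusted difference to remove the tilt.

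*SAP*

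**What the plan says.** **Entry.** Protocol 4.1, criterion 4: "On Day -1, subjects must have a mean IOP of ≥ 24 mmHg at 8:00 AM and a mean IOP of ≥ 22 mmHg". The second threshold applies to the 10:00 AM reading. One qualifying eye is enough, and the two eyes must be within 4 mmHg of each other. Protocol 4.2 adds an upper limit: "Subject has IOP greater than 32 mmHg in either eye before randomization".

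**Study eye.** Protocol 3.1.1 and SAP 2.4 choose the eye with the higher predose mean over Days -2 and -1.

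**Baseline.** SAP 12.4: "Baseline is defined as the arithmetic mean of the time-matched IOP measurements on Days -2" and -1. SAP 11.6.2.9 uses the same definition, one baseline per time point.

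**Cohort A.** Criterion 4 ties the selection to the single-dose period (SDTP): "this eye will also be used for dosing in Cohort A SDTP". Subjects are randomized before the single dose, once the entry criteria are confirmed (Protocol 3.1.4.1), and not again (Table 1, footnote i). SAP 2.4 adds: "For Cohort A, the study eye for MDTP will be the same as the study eye in SDTP". The multiple-dose (MDTP) baseline is a new Day -2/-1 pair after a 3-14 day washout.

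**Cohorts B-D.** There is one Day -2/-1 pair, and randomization follows on MDTP Day 1 (Protocol 7.1.2.2).

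**Analysis.** SAP 12.5 plans "Descriptive summary statistics for absolute IOP, IOP reduction from baseline, percentage of IOP reduction from baseline" and the derived PD parameters, with 95% CIs, by dose and cohort. It names no difference from placebo and does not say how placebo is grouped. SAP 11 pools MDTP placebo within each regimen for ocular summaries; SAP 4.3 and Protocol 9.9.2 describe a single pooled placebo group.

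**The concern.** A subject admitted because one reading was high will tend to read lower next time, and so will an eye chosen because it was the higher of two. If the selecting readings also serve as baseline, part of this fall is counted as IOP reduction. In Cohorts B-D they do; in Cohort A's MDTP the baseline is measured after the selection. The same baseline definition thus yields a selected baseline for BID, TID and QID and a largely unselected one for QD.

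The secondary objective is to "evaluate reduction of IOP, as a PD biomarker, following different SHP639 dosing regimens", so readers will set the regimens side by side. On raw change from baseline, QD starts at a small disadvantage unrelated to the drug. A larger sample does not shrink this.

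**Working it through.** The plan states no figure for this effect, so there is none to reproduce. The check is a simulation with no drug effect.

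**From the documents:** the 24 and 22 mmHg thresholds on Day -1; inter-eye difference under 4 mmHg; the 32 mmHg cap; the higher-eye rule; baseline as the Day -2/-1 mean; 5:2 allocation.

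**Assumed (not in the documents):** screened mean 8 AM IOP 20-26 mmHg; between-subject SD 2-4; within-subject day-to-day SD 1-3; between-eye SD 1; between-eye error correlation 0.7; within-day error correlation 0-0.6; true IOP 1, 1.5 and 2 mmHg lower at +2, +4 and +8 h; errors independent between days. I take 8 AM as predose and 10 AM as +2 h.

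**Quantity:** mean of (baseline minus a later on-treatment reading) in the study eye of eligible subjects. For B-D, baseline is the selecting pair of days; for Cohort A MDTP it is a later pair in the same eye.

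**Mid case** (within-subject SD 2, between-subject SD 3), spurious reduction in B-D in mmHg:

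| Screened mean | Within-day correlation | Predose | +2 h | +4 h | +8 h |
|---|---|---|---|---|---|
| 22 | 0 | 0.56 | 0.25 | -0.01 | -0.01 |
| 22 | 0.6 | 0.68 | 0.51 | 0.44 | 0.45 |
| 25 | 0 | 0.37 | 0.09 | -0.03 | -0.01 |
| 25 | 0.6 | 0.40 | 0.27 | 0.25 | 0.26 |

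Cohort A MDTP is 0.0 in every row. With the 10 AM value 1.5 mmHg below 8 AM and screened means of 23 and 25, predose was 0.35-0.57, hence about 0.3-0.7 for the mid case. On the percent scale the predose gap from Cohort A in the two correlated rows is 2.55 - (-0.30) = 2.9 and 1.41 - (-0.28) = 1.7 percentage points.

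**Full assumed range, B-D:** 0.11 to 1.52 mmHg at predose; 0.01 to 1.25 at +2 h; -0.14 to 1.03 at +4 and +8 h, essentially zero there when within-day errors are uncorrelated.

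**Against sampling error:** the simulated SD of change in the mid case is about 2.4 mmHg.
- One 5-subject group: SE = 2.4/√5 = 1.07; 95% CI half-width 2.776 × 1.07 = 3.0.
- All 21 subjects of a regimen, which SAP 11 also displays: SE = 2.4/√21 = 0.52, about the size of the bias.

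**Does placebo remove it?** Let b be the bias in B-D.
- Same-regimen placebo: b - b = 0 in B-D and 0 - 0 = 0 in QD.
- One pooled placebo group: planned placebo numbers are 6 (QD), 6 (BID), 6 (TID) and 4 (QID without D1), 22 in all, so its mean bias is (16/22)b = 0.73b. QD active minus pooled placebo is then -0.73b and B-D active minus pooled placebo is +0.27b. The gap is still b. For b = 0.68 the two values are -0.49 and +0.19 mmHg.

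**The case against.** **Placebo by regimen is already planned in one place.** SAP 11 pools MDTP placebo by regimen for ocular summaries, and the IOP tables of SAP 11.6.2.9 are among them. An inactive drug would show the same fall in the placebo column beside it. This stands, and it supplies much of the remedy. What is missing is the same rule in SAP 12.5, agreement with the single pooled group of SAP 4.3 and Protocol 9.9.2, and an actual difference with a CI.

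**The interim analyses.** A reader might infer that they relied on tables with no matched placebo. The SAP 16 list does not support that: the SAP 12.5 tables (14.2.3.2.1 and .2) are marked as not produced at interim, while the MDTP IOP tables that are (14.3.7.9.7-.12) fall under SAP 11.

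**A false dose-frequency response.** A reader might infer one. B, C and D share the same selection, so the artefact is a single step from QD to the rest, not a gradient.

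**No regimen comparison is planned.** Correct: the objective is to evaluate reduction under different regimens, the analyses are descriptive, and no test between regimens is specified. The tilt affects interpretation, not a type I error rate.

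**Cohort A may be re-qualified.** Table 1 marks an eligibility check at MDTP Day -2 without exempting Cohort A. That precedes the Day -1 reading, but B-D also have their last marked check on Day -2, so the table settles nothing. With re-qualification, Cohort A's mid-case predose bias would be 0.07-0.25 mmHg, leaving a gap of about 0.3-0.4 in the same direction.

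**The size is fragile.** It is: every SD is assumed, and the zero for Cohort A follows from assuming independent errors across the washout.

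**Conclusion.** The asymmetry and its direction follow from the documents. Its size does not: roughly 0.1-1.5 mmHg at predose under the assumed SDs, about 0.3-0.7 in the mid case, less at +2 h, and near zero later unless within-day errors are correlated.

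It is a one-step tilt of QD against the other regimens, confined to raw comparisons across regimens and usually below the standard error of a 5-subject cohort. SHP639 against placebo of the same regimen is unbiased. The documents do not support the stronger claim that the planned tables would rank the regimens falsely, or that the plan has no matched control. The point is worth acting on because the bias is systematic and foreseeable, and the data that remove it are already collected.

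**What to change.** In SAP 12.5:

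1. Apply the by-regimen placebo pooling of SAP 11 to the PD analyses. For IOP, do not pool Cohort A placebo with B-D placebo, and reconcile this with SAP 4.3 and Protocol 9.9.2.
2. For each dose and regimen, add the SHP639-minus-same-regimen-placebo difference in time-matched IOP change and percent change, with a 95% CI. Read comparisons across regimens from these differences.
3. State whether criterion 4 was applied again to Cohort A before the MDTP.
4. Optionally, show Cohort A MDTP change against its SDTP Day -2/-1 baseline, which carries the same selection as B-D.

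**Cost:** one table and a few sentences. The intervals will be wide. There are about 4-6 placebo subjects per regimen, or about 8 for BID if the repeat of B3 was also randomized 5:2. At the assumed SD of 2.4 mmHg, 5 active against 6 placebo gives SE = 2.4 × √(1/5 + 1/6) = 1.45 and a half-width of 2.262 × 1.45 = 3.3 mmHg. Against 4 placebo the SE is 1.61 and the half-width 2.365 × 1.61 = 3.8 mmHg.

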12.5 Statistical Analysis of Pharmacodynamic Data

Absolute IOP, IOP reduction from baseline, and percentage of IOP reduction from baseline will be listed by dose, cohort, subject, treatment period (single dose or multiple dose; Cohort A only), eye (study eye and non-study eye), study day and sample nominal time point. Descriptive summary statistics for absolute IOP, IOP reduction from baseline, percentage of IOP reduction from baseline, E_{max}, TE_{max}, AUEC_{0-t}, AUEC_{0-τ}, and AUEC_{0-∞} (n, arithmetic mean, SD, 95% CI, median, maximum, minimum, geometric mean and geometric CV%) will be calculated by dose, cohort, treatment period, eye (study eye and non-study eye), study day, and sample nominal time point (for days with multiple assessments per day).

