9.8.2.2 Statistical Analysis of Pharmacodynamic Parameters

Descriptive summary statistics for IOP (number of subjects, mean, SD, median, min, and max) will be calculated by dose, cohort, treatment period (single dose or multiple dose; Cohort A only), study day, and time point (for days with multiple assessments per day). Additionally, 95% CIs for each estimate and summary statistics of change from baseline and percentage change from baseline, along with 95% CIs, will be calculated. Pharmacodynamic parameters will be calculated and summarized by dose, cohort, treatment period (single dose or multiple dose; Cohort A only), and study day as applicable.

All IOP data will be listed by dose, cohort, subject, treatment period (single dose or multiple dose; Cohort A only), and study day.

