^m Drop comfort assessments will be performed immediately and 1, 2, and 3 minutes after instillation of the investigational product; to be assessed at morning doses only. If the score is not ≤ 3 at minute 3, the drop comfort assessment should be repeated at minutes 5, 10, and 15 until the score is ≤ 3 . If the score is >3 at minute 15, it should be recorded as an adverse event.

ⁿ If BCVA decreases by 6 or more letters, then a dilated posterior segment examination should be performed.

^o Manifest refraction should be repeated if the BCVA in either eye decreases by 10 or more letters.

^p Conjunctival redness will be evaluated using the Efron scale.

^q SDTP dosing (Cohort A only): investigational product (SHP639 ophthalmic solution or placebo) will be administered once on the morning of Day 1. MDTP dosing: Cohort A=once daily, Cohort B=twice daily, Cohort C=3 times daily, Cohort D=4 times daily; the final dose will be administered on the morning of Day 28. Dose administration will occur during waking hours.

^r The Day 88 visit is 60 days post last dose (Day 28 of MDTP).

^s For Screening, MWOA, and Day 29 visits only one round of ophthalmic assessments needs to be done in the morning.

^t At check-in for overnight stays the following assessments will be performed: physical exam, drugs of abuse screening, alcohol breathalyzer, vital signs, hematology, chemistry, urinalysis, and a single ECG.

^u The Day 88/FU visit is labeled "Day 88" based on a subject's duration of participation from Day 1 (1st dose) of the MDTP. Subjects in cohort A1, A2, and A3 will have been in the study for a longer duration due to the SDTP.

^v At screening IOP may be done at any time during the day. At MWOA (D-14), IOP should be done at 10:00am +3 hours. IOP only needs to be done at one time during screening, MWOA, and Day 29.

Table 2 Detailed Schedule of Events – Cohort A

Assessment	Days Performed (Screening-D29) ^f	Predose/ Morning ^a	0 m	30 m	1 h	2 h	3 h	4 h	6 h	8 h	12 h
		Gonioscopy ^c	SCR, D29.	X							
Specular microscopy, noncontact	SCR. SDTP: D-1, D2. MDTP: D-1, D14, D29.	X									
Corneal pachymetry	SCR. SDTP: D-1, D1, D2. MDTP: D-1, D1, D2, D7, D14, D29.	X			X	X		X			X
Antidrug Ab blood sampling	D-2, D14, D29, D88/FU	X									
Drugs of abuse	SCR, D-14, SDTP: D-2, MDTP: D-2 and D-1, D1, D14, D21, D26.	X									
Alcohol breath test	SCR (D-42), SCR (D-14). SDTP: BL (D-2), MDTP: BL (D-2 and D-1), D1, D14, D21, D26.	X									

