12.2.3 Pharmacokinetic Parameters

The following plasma PK parameters will be calculated for SHP639 on Day 1 for SDTP (Cohort A only) and on Day 1 and Day 27 for MDTP (all cohorts) by non-compartmental method using Phoenix[®] WinNonlin[®] version 6.4 or higher (Certara USA, Inc., Princeton, NJ).

Parameter	Definition
C_{max}	Maximum observed plasma concentration
T_{max}	Time to reach maximum observed plasma concentration
$AUC_{0-\infty}$	Area under the plasma-concentration time curve from time 0 extrapolated to infinity, calculated using the linear up/ log down trapezoidal rule
AUC_{0-t}	Area under the plasma-concentration time curve from time 0 to the last measurable concentration, calculated using the linear up/ log down trapezoidal rule
$AUC_{0-\tau}$	Area under the plasma-concentration time curve over a dosing interval for each multiple-dose regimen, calculated using the linear up/log down trapezoidal rule (Day 1 and Day 27 for MDTP of all cohorts)
$t_{1/2}$	Apparent first-order terminal elimination half-life, calculated as $t_{1/2} = \ln 2 / K_{el}$
K_{el}	Elimination rate constant estimated from the linear regression of the natural log-transformed concentration over time at the terminal phase.
$\%AUC_{ex}$	Percentage of the area extrapolated for calculation of $AUC_{0-\infty}$
CL/F	Apparent clearance, calculated as $Dose / AUC_{0-\infty}$ for Day 1 for SDTP (Cohort A only) and $Dose / AUC_{0-\tau}$ for Day 27 for MDTP (all cohorts)
V_z/F	Volume of distribution, calculated as $V_z/F = (CL/F) / \lambda_z$
$R_{ac}(C_{max})$	Accumulation ratio based on C_{max} for each multiple-dose regimen, calculated as $C_{max} (Day 27) / C_{max} (Day 1)$
$R_{ac}(AUC)$	Accumulation ratio based on AUC for each multiple-dose regimen, calculated as $AUC_{0-\tau} (Day 27) / AUC_{0-\tau} (Day 1)$

All calculations for PK analysis will be based on actual sampling times. All PK analyses will be conducted by the Department of Clinical Pharmacology, PPD, Inc, Richmond, VA, USA.

All PK parameters will be presented in data listings and summarized in tables by dose, cohort, treatment, and study day, using descriptive statistics (n, mean, SD, median, maximum, minimum, geometric mean, and CV%). Geometric means will be reported for AUCs and C_{max} only.

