AUEC _{0-∞}	Area under the effect curve for the percentage of IOP reduction from baseline versus time profile from time zero (predose) extrapolated to infinity, calculated using the linear up/log down interpolation rule.

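### SAP 12.4–12.5 apply geometric statistics, log-down areas and extrapolation to infinity to IOP reductions that can be zero or negative, with no rule for such values

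*SAP*

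**What the plan says.** SAP 12.4 defines percentage IOP reduction as baseline minus post-treatment IOP, divided by baseline, times 100. Baseline is the time-matched mean of Days -2 and -1. From that profile it derives Emax, TEmax and three areas under the effect curve. AUEC0-tau is taken from the percentage reduction "versus time profile over a dosing interval, calculated using the linear up/log down interpolation rule"; AUEC0-inf runs "from time zero (predose) extrapolated to infinity, calculated using the linear up/log down interpolation rule"; AUEC0-t uses the same rule.

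SAP 12.5 then applies one list of statistics to absolute IOP, both reductions, Emax, TEmax and every AUEC. The list ends "median, maximum, minimum, geometric mean and geometric CV%) will be calculated by dose, cohort, treatment period, eye (study eye and non-study eye").

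Other parts of the documents are narrower:

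- SAP 12.2.3, for pharmacokinetics: "Geometric means will be reported for AUCs and C_{max} only". Tmax therefore gets no geometric mean, while TEmax does.
- Protocol 9.8.2.2: "Descriptive summary statistics for IOP (number of subjects, mean, SD, median, min, and max) will be calculated by dose, cohort", with 95% CIs and change from baseline added, and no geometric statistics. SAP 15.1 lists none either.
- The only rule for low values in SAP section 12 (12.2.2) concerns plasma concentrations below the limit of quantification.

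**The concern.** A geometric mean, a geometric CV%, a log-down segment and a log-linear terminal slope all need positive values. A reduction from baseline is not confined to positive values. It is near zero on average wherever there is no drug effect: possibly on placebo, in the undosed eye of the Cohort A single-dose period, and at the Day 1 predose reading. TEmax equals 0 h when the largest reduction falls at predose.

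Neither SAP 12.4, 12.5 and 15 nor protocol 9.8.2 says whether such values are dropped, replaced, handled by a linear segment, or left to make the result missing. The statistic would then be undefined or would depend on a choice made at programming. IOP reduction is the secondary objective. The outputs concerned are Tables 14.2.3.2.1 and 14.2.3.2.2, which SAP 16 marks as not part of the interim analyses.

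**Working it through.** The plan gives no figure to reproduce, and the documents give no SD or expected size for IOP change. SDs, true effects, normality and a constant effect over time are assumptions below.

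**1. Can the values be non-positive within protocol limits?** IOP is read to the nearest mmHg (SAP 11.6.2.9). Entry on Day -1 needs at least 24 mmHg at 8:00 AM (protocol 4.1), the ceiling before randomization is 32 mmHg (4.2), and withdrawal applies above 36 mmHg (4.5.1).
- 24 to 24: 0%
- 24 to 25: (24 − 25)/24 × 100 = −4.17%
- 32 to 36: (32 − 36)/32 × 100 = −12.5%

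**2. Geometric mean of one hypothetical cell: 12, 8, 15, 10, −2%.** The arithmetic mean is 43/5 = 8.6. The geometric mean is undefined as written. By convention it becomes:
- −2 dropped: (12 × 8 × 15 × 10)^(1/4) = 10.95
- −2 set to 1: (14400 × 1)^(1/5) = 6.79
- −2 set to 0.1: (14400 × 0.1)^(1/5) = 4.28

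**3. How many cells are touched?** The multiple-dose schedule in 12.4 is "Days 1, 2, 27, and 28, at Predose, 0.5, 1, 2, 3, 4, 6, 8, and 12 h" (the line carries both a Cohort A and an all-cohorts label; I read it as all cohorts) and "MDTP (all cohorts): Days 7, 14, and 21 at Predose, 2, 4, 8, and 12 h". Per group and eye that is 4 × 9 + 3 × 5 = 51 cells. The chance that a cell of n subjects holds a value at or below zero is 1 − (1 − Φ(−mu/SD))^n.

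| True mean | n | SD 6 | SD 8 | SD 10 |
|---|---|---|---|---|
| 10% | 5 | 0.217 | 0.428 | 0.578 |
| Expected cells of 51 | | 11.1 | 21.8 | 29.5 |
| 14% | 5 | 0.048 | 0.185 | 0.344 |
| Expected cells of 51 | | 2.5 | 9.4 | 17.5 |

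With no true change, half of single values are at or below zero whatever the SD, so 0.75 of cells with n = 2 and 0.984 with n = 6 are touched. The counts use one mean for all 51 cells, although Day 1 predose precedes treatment.

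**4. Positives-only geometric mean under no effect.** exp(E[ln X | X > 0]) for X normal with mean 0 gives 3.18, 4.24 and 5.30% at SD 6, 8 and 10.

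**5. Log-down segment.** The area is (t2 − t1)(c1 − c2)/ln(c1/c2). From 8 to 12 h:
- 10 to 5%: 28.85 (linear 30)
- 10 to 0%: the log is infinite and the area collapses to 0 (linear 20)
- 10 to −4.17%: undefined (linear 11.66)

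I simulated 200,000 nine-point profiles with (between, within) SDs of (5, 6) and (6, 8), so total SDs of √61 = 7.8 and √100 = 10. The share with at least one falling segment ending at or below zero is 0.917 and 0.930 at no effect, and 0.400 and 0.563 at a 10% reduction. The ratio of two negative values can be evaluated. Counting only segments that cross from positive to non-positive gives 0.825 and 0.854 at no effect, and 0.398 and 0.556 at 10%.

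**6. Emax and TEmax.** In the same model Emax is at or below zero in about 6–7% of no-effect profiles and about 0.1% at a 10% reduction. By exchangeability, TEmax falls at predose in 1/9 of no-effect nine-point profiles and 1/5 of five-point profiles.

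**The case against.** The strongest reply is that little is lost. The analyses are descriptive (SAP 2.3). The arithmetic mean, SD, 95% CI and median are planned alongside, and the safety-set IOP tables in SAP 11.6.2.9 do not use the affected operations. The protocol has PD parameters estimated as appropriate (9.8.2.1), and output specifications sit in a separate document (SAP 1) that is not available here. This stands as a limit on severity. It does not supply a rule: discretion is not a convention, and 12.5 orders the geometric statistics without exception.

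Four stronger readings are tempting and not supported:

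- **The active–placebo difference would be biased.** Dropping non-positive values would distort such a difference, but neither document plans a contrast of geometric means or says that values are dropped.
- **Emax fails generally.** On active drug with a real effect it is almost always positive. The problem lies mainly in no-effect groups.
- **AUEC0-tau cannot be computed on many days.** A nominal 6 h QID interval on Days 7, 14 and 21 is bracketed by the 4 h and 8 h readings, and a once-daily Day 28 interval can be closed by the Day 29 morning IOP listed in SAP 11.6.2.9. Only once-daily Days 2, 7, 14 and 21 lack a reading near 24 h.
- **A fixed, small share of profiles could be extrapolated.** That share depends on the assumed time course. At an average 14% reduction it is 39–44% with a constant effect and about 50–63% with a rise and fall. The case against AUEC0-inf is that it exists only for profiles that end positive and falling, not any particular percentage.

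**Conclusion.** The point holds for IOP reduction, percentage reduction, TEmax and the AUECs, and for Emax chiefly where there is no effect. As written, the geometric statistics, the log-down areas and AUEC0-inf fail on data the design makes foreseeable, and no rule covers them. Under no true change about half of single values are non-positive, whatever the SD. The other sizes rest on assumed SDs of 6–10 percentage points, normality and a constant effect; a larger effect shrinks them, as the 14% rows show.

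A reader might infer that the secondary objective cannot be assessed. The documents do not support that: absolute IOP, the arithmetic summaries and the safety-set tables remain sound. Severity is minor to moderate, confined to descriptive outputs of the secondary objective.

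**What to change.** **SAP 12.5.** Keep geometric mean and geometric CV% for absolute IOP only. Summarise reduction, percentage reduction, Emax, TEmax and the AUECs by arithmetic mean, SD, 95% CI and median. Protocol 9.8.2.2 already takes this approach for IOP, so no protocol commitment is broken.

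**SAP 12.4.**
- Compute AUECs by the linear trapezoid on the signed percentage reduction, counting negative areas as negative, over the scheduled readings. Include Day 2 of the single-dose period, where readings continue after the one Day 1 dose.
- Delete AUEC0-inf.
- Report AUEC0-tau wherever readings reach or bracket the end of the interval, with linear interpolation. State the nominal tau used for each regimen, because 12.4 gives none and footnote q to SAP Table 1 says only "Dose administration will occur during waking hours".

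**Cost.** SAP wording and modest programming, with no extra data. One limit remains: a once-daily 24 h area rests on a single 12–24 h segment.
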